2. STUDY OBJECTIVES AND ENDPOINTS

2.1 Objectives

2.1.1 Primary Objective

To determine the efficacy of intranasal ketorolac (sprix) in decreasing the acute pain of patients in the emergency department (ED)

2.1.2 Secondary Objective

To determine the safety and tolerability of intranasal ketorolac (sprix) in decreasing the acute pain of patients in the emergency department (ED)

2.2 Variables

2.2.1. Primary Efficacy Variable

The primary efficacy variables are the pain measurements after the administration of the intranasal ketorolac (sprix) as compared with the baseline pain scales. Pain scales to be used are the Numeric Rating Scale (NRS) where 0 = no pain and 100 mm = worst pain possible and the global assessment of pain (using a 5 point Likert scale) and the global assessment of analgesia (pain relief) (using a 5 point Likert scale) (See appendix 1)

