5.1.4.2 Study Pain Assessments

Study pain assessments will be done before and after the administration of the single dose of intranasal ketorolac (sprix). All patients will have a minimum of two pain scores (NRS): a baseline (pre administration of the intranasal ketorolac) and a post administration of intranasal ketorolac. The time that the pain score is done, whether at baseline or post intranasal administration of the ketorolac, will be recorded any time a baseline or post-treatment NRS pain score is done. A post-treatment NRS pain score will be done immediately prior to the patient leaving the ED and immediately prior to the patient receiving rescue medication (e.g. any additional pain medication or sedatives) with the time post-treatment to be recorded. Depending on the length of time the patient is in the ED, additional NRS pain scores will be done, if possible. While the patient is in the ED, additional NRS pain scores will be recorded at specified times after study drug administration; specifically, at 20 minutes, 40 minutes, 1 hour, 2 hours, 3 hours, 4 hours, 5 hours and 6 hours for as long as the patient remains in the clinical site, in addition to time 0 (baseline = before administration of the study drug). (See Appendix 1) The pain scores will be compared and analyzed for statistical significance comparing the baseline (pre-study drug administration) with the "post-study drug administration or "treatment" pain scores.

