6.2 Efficacy Variables

6.2.1 Primary Efficacy Variable

- The primary efficacy variable is the assessment of pain by the NRS after the administration of intranasal ketorlac (sprix).

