6.2.2 Secondary Efficacy Variables

The secondary efficacy variables are the global pain assessment scores, the global assessment of analgesia (pain relief) scores, the patient questionnaire and the health care provider questionnaire which are completed before the patient leaves the clinical site (e.g. ED).

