Appendix 1B: Global Pain Assessment Scale

How would you rate your pain?

0 = none 1 = a little (mild) 2 = some (moderate) 3 = severe
4 = very severe (extreme)

**Appendix 1C: Global Assessment of Analgesia
(Global Assessment of Pain Relief)**

How would you rate your pain relief?

0 = poor 1 = fair 2 = good 3 = very good 4 = excellent

**Appendix 1D: Calculated Pain Assessments:
Pain Intensity Difference (PID)
Summed Pain Intensity Difference (SPID)
(Weighted Sum of PID)
Total Pain Assessment Relief (TOTPAR)
(Weighted sum of pain relief scores)**

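### Section 2.2.1 lists three primary scales where 6.2 has only the NRS, and no readable passage says which post-dose NRS score is the primary one

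*Combined protocol and SAP*

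**What the plan says.** **Primary variable.** Section 2.2.1 is in the plural: "The primary efficacy variables are the pain measurements after the administration of the intranasal ketorolac (sprix) as compared with the baseline pain scales". The scales it lists are the NRS, the global assessment of pain and the global assessment of analgesia. Section 6.2.1 is in the singular: "The primary efficacy variable is the assessment of pain by the NRS after the administration of intranasal ketorlac (sprix". Section 6.2.2 then states: "The secondary efficacy variables are the global pain assessment scores, the global assessment of analgesia (pain relief) scores", followed by the two questionnaires. Section 7.1 bases the sample size on the PID, defined there as post-treatment NRS minus baseline NRS.

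**Post-dose scores.** Section 5.1.4.2 sets a floor: "All patients will have a minimum of two pain scores (NRS"), one before and one after dosing. It adds that a post-treatment "NRS pain score will be done immediately prior to the patient leaving the ED and immediately prior to the patient receiving rescue medication". Beyond that, "additional NRS pain scores will be done, if possible", and the schedule is "specifically, at 20 minutes, 40 minutes, 1 hour, 2 hours, 3 hours, 4 hours, 5 hours and 6 hours" for as long as the patient stays. Section 5.1.6.1 repeats this.

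**Analysis.** Section 7.2 compares scores before and after treatment by a t-test or an F-test, with significance at p=0.05. It names no post-dose time and no rule for combining times. Section 7.1 gives 25 patients, 80% power and effect size 0.56 (mean PID divided by its SD), with no time attached.

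**The concern.** The plan has two defects in its primary variable.

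First, the two definitions disagree about the global scales. The comparison in 2.2.1 also cannot be carried out for one of them. The Appendix 1C item asks "How would you rate your pain relief", which has no meaningful answer before the drug is given, so it has no baseline to compare with.

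Second, the NRS itself is not pinned to an assessment. A patient may have up to ten post-dose scores, and no readable section says whether the claim rests on a fixed time, the last score, the score before rescue, or some summary. If that is settled after the data are seen, the most favourable time can be chosen, and with it the number of patients who contribute. The effect size behind the sample size also cannot be assigned to any one assessment.

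**Working it through.** **1. The definitions side by side**

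| Scale | 2.2.1 | 6.2.1 / 6.2.2 | 7.1 |
|---|---|---|---|
| NRS | primary | primary | basis of the PID used for power |
| Global pain assessment | primary | secondary | not used |
| Global assessment of analgesia | primary | secondary | not used |

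Sections 6.2 and 7.1 agree on the NRS; 2.2.1 stands alone.

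**2. Candidate scores.** Eight scheduled times + one before rescue + one before departure = up to 10. Only one post-dose score is assured for every patient, and it is not called primary. A rescued patient can have both a pre-rescue and a pre-departure score.

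**3. The plan's power.** Inputs from 7.1: n = 25, effect size d = 0.56. Significance at 0.05 is from 7.2. Two-sidedness is inferred, because 7.1 tests for a difference from zero.
- Normal approximation: power = Φ(d√n − 1.96) = Φ(0.56 × 5 − 1.96) = Φ(0.84) = 0.800. Inverted, n = ((1.96 + 0.8416)/0.56)² = 25.03. This reproduces the plan's figure.
- One-sample (paired) t-test: 24 degrees of freedom, critical value 2.064, noncentrality 0.56 × 5 = 2.8. Power = 0.766.
- For 80% by t-test at d = 0.56: n = 27 gives 0.7998 and n = 28 gives 0.815. With n = 25, d would have to be 0.584.

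**4. Effect of choosing the time afterwards (illustration).** The documents give no correlations between times and no patient counts by time, so both are assumed. Model: PID for patient i at time j is √ρ·uᵢ + √(1−ρ)·eᵢⱼ, standard normal, mean zero, with 25 patients scored at every time considered. At each time, t = mean/(SD/5), and a false improvement is a t beyond 2.064 in the favourable direction. With 100,000 simulated trials per correlation, the chance of at least one is:

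| Times to choose from | ρ = 0.5 | ρ = 0.7 | ρ = 0.9 |
|---|---|---|---|
| One named score | 2.5% | 2.5% | 2.6% |
| First three (20, 40, 60 min) | 6.4% | 5.5% | 4.2% |
| All eight | 12.7% | 9.7% | 6.1% |

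Repeat runs agree to within about 0.2 percentage points. The one-score row is a check against 0.05/2 = 2.5%.

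**5. Effect on the number analysed.** If 20, 15 or 10 patients had a score at the chosen time (assumed counts), t-test power at d = 0.56 would be 66%, 52% or 35%, against 77% with all 25. Section 5.6 says that patients who discontinue are not replaced.

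**The case against.** **The NRS is plainly meant.** The definitions section says so in the singular, the sample size uses NRS differences, and the scale list in 2.2.1 can be read as a list of instruments. This stands. A reader might infer that the trial has three co-primary scales with no multiplicity control. The documents do not support that: two of the three relevant sections point to the NRS alone. What remains is an outlying section that needs correcting.

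**Zero mean change is unlikely.** This is an unblinded single-arm study of patients who enter with NRS of at least 40 on the 0 to 100 scale and may receive opioids. In the trials summarised in 1.2, placebo groups also improved (6-hour SPID of 89.9, 76.7, 37.2 and 130.6), although those were post-operative and several allowed patient-controlled morphine. This stands as a limit on the illustration. If pain fell for non-drug reasons with an assumed effect size of 0.2, 0.3 or 0.4, one pre-named t-test with 25 patients would be significant 16%, 30% or 48% of the time. So 2.5% is not the risk of wrongly crediting the drug. Naming one score still fixes the estimate and the number analysed.

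**The eight-time figure is an upper end.** It requires all 25 patients to stay six hours, while the plan collects scores only during the stay and where possible. This stands. The first-three-times range is easier to defend.

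**The time may be stated elsewhere.** Figure 1 and the content of Appendix 1A are not shown. The point about the primary score is therefore limited to the readable text. The conflict between 2.2.1 and 6.2 does not depend on them.

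**Conclusion.** The point holds. The primary definition conflicts between 2.2.1 and 6.2, with 2.2.1 the outlier, and its baseline comparison is not possible for the pain-relief item. In the readable text, no one of up to ten post-dose NRS scores is named as primary.

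The size is moderate and illustrative: a false-improvement rate of about 6.4% to 4.2% over the first three times, and at most about 13% to 6% over all eight, against 2.5%. These figures rest on zero mean change, two-sided 0.05 tests, correlations of 0.5 to 0.9 and 25 patients scored at each time.

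A reader might go on to infer that naming a score would make a positive result evidence of a drug effect. With no control group, it would not. A reader might also infer that 25 patients is a miscalculation. It is not: the stated 80% reproduces under the normal approximation, and the t-test figure of about 77% is a separate and smaller refinement.

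This should be fixed before any data are seen, because a choice made afterwards cannot be undone.

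**What to change.** 1. Make the abstract, 2.2.1, 2.2.2, 6.2, 7.1 and 7.2 agree on one primary variable: NRS change from baseline at one post-dose assessment that the sponsor names before any data are seen. Use one sign convention for the PID; 7.1 takes post minus baseline, while most of the study summaries in 1.2 take baseline minus post. Move both global scales to secondary, with pain relief assessed post-dose only.
2. If a scheduled time is named, state in 7.2 that patients who leave or receive rescue earlier are analysed with the pre-departure or pre-rescue NRS already collected. Add a sensitivity analysis of scores observed at that time, and say whether scores taken after rescue count in it.
3. If the score assured for every patient is named instead, state which score counts for a rescued patient and report the distribution of its time after dosing.
4. In 7.2, specify a paired t-test at two-sided 0.05 for this comparison. Present the other times as supportive, with estimates and 95% confidence intervals.
5. In 7.1, tie effect size 0.56 to the named assessment and restate power as about 77% with all 25 patients scored.

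Optional tidying: give 2.2.2 and 6.2.2 one secondary list, and say whether need for additional pain medication (5.1.4.4) and TOTPAR (Appendix 1D) belong in it.

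The cost is wording only, with no new data. A scheduled time needs an assumption for patients without a usable score then. The assured score falls at different times after dosing in different patients. The stated power is slightly lower because of the t-test calculation, not because one endpoint is named.

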2.2.2 Secondary Efficacy Variable

The secondary efficacy variables are additional (calculated) pain measurements after the administration of the intranasal ketorolac (sprix). This will include the pain intensity difference (PID) and the summed pain intensity difference (SPID) (See appendix 1)

2.2.3 Safety Variables

2.2.3.1 Primary Safety Variables

The primary safety variables are the occurrence of adverse events (after the intranasal ketorolac has been administered)

2.2.3.2 Secondary Safety Variables

The secondary safety variables are the vital signs taken after the intranasal ketorolac has been administered. An additional secondary safety variable is the appearance of the nasal mucosa after the administration of the intranasal ketorolac, sprix.

3. INVESTIGATIONAL PLAN

3.1 Overall Study Design and Plan

This is a prospective, nonblinded, efficacy, safety and tolerability trial in non-geriatric adults (from age 18 to 64 years) who are in the emergency department (ED) being treated for moderate to severe acute pain (e.g. NRS ≥ 4 on a 0 to 10 NRS or ≥ 40 on a 0 to 100 NRS). Written consent is obtained from the patient. Eligible subjects will be enrolled.

3.2 Study Population

3.2.1 Description

Adult non-geriatric (ages 18 to 64 years) subjects who present to the emergency department (ED) in moderate to moderately severe acute pain (e.g. NRS ≥ 4 on a 0 to 10 NRS or ≥ 40 on a 0 to 100 NRS) from an acute illness or injury (such as a kidney stone or an acute musculoskeletal injury) are eligible for enrollment in the study

3.2.2 Inclusion Criteria

A patient is eligible for enrollment into the study if all of the following criteria (and none of the exclusion criteria) are met:

1. Patient is being seen in the emergency department (ED) in acute pain from an acute illness or injury (such as a kidney stone or an acute musculoskeletal injury)
2. Age ≥ 18 years and < 65 years
3. Stable patient with stable vital signs, including not in shock (systolic BP >90), not in respiratory failure, and not a multiple trauma patient
4. Mentally competent patient is able to understand the consent form
5. Baseline pain score is moderate to severe (e.g. on NRS ≥ 4 on a 0 to 10 NRS or ≥ 40 on a 0 to 100 NRS)

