4.2 Method for Application of Ketorolac (Sprix) for the Treatment of Acute Pain

After identifying appropriate adult patients (see section 3.2), obtaining written consent (see section 9.3), and performing all pre-dose (baseline) pain assessments, ketorolac (Sprix) will be administered in the standard fashion.

A single dose of 31.5 mg will be administered with one 15.75 mg spray (in a metered dose of 100 µL per spray) in each nostril for a total of two intranasal sprays per patient that total 31.5 mg in 200 µL. Note: The time at which the second intranasal spray administration is completed is time 0. As stated above, the baseline pain assessments will be completed prior to the administration of the intranasal ketorolac (sprix).

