7. DATA ANALYSIS AND STATISTICAL METHODOLOGY

7.1 Planned Sample Size

Since this is a prospective, efficacy and safety trial, the planned enrollment is for 25 patients who will receive a single dose of intranasal ketorolac. This sample size provides 80% power to demonstrate that the mean pain intensity to demonstrate that the mean pain intensity difference (PID), (where the PID = post-treatment NRS – baseline NRS) differs from zero when the effect size is 0.56. The effect size was calculated as the mean PID divided by the standard deviation.

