7.2 Efficacy

The pain scores pre and post-treatment (after administration of the intranasal ketorolac [sprix]) will be compared. Pain scales are a continuous variable. Therefore, pain scales and other pain assessments (such as PID, SPID) (all continuous variables) will be compared using t-test or F-test.

The questionnaires (patient and health care provider) are discrete variables and will be compared using chi-square or Fischer's exact test.

Significance is at $p=0.05$.

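### The pain score that qualifies a patient may also be the only baseline for PID, so regression to the mean can be counted as drug effect

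*Combined protocol and SAP*

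**What the plan says.** Section 3.2.2, criterion 5, reads "Baseline pain score is moderate to severe", with 4 on a 0 to 10 scale or 40 on a 0 to 100 scale as the lower limit. The word used for the qualifying score is therefore baseline.

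Section 5.1.4.2 sets the minimum data: "All patients will have a minimum of two pain scores (NRS): a baseline (pre administration of the intranasal ketorolac") and one score after dosing. No section names a separate screening score.

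Section 4.2 gives the order of events: identify suitable patients, obtain consent, then, after "performing all pre-dose (baseline) pain assessments, ketorolac (Sprix) will be administered in the standard fashion".

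Section 7.1 defines "PID = post-treatment NRS – baseline NRS" and sizes the trial for 80% power, with 25 patients, to show that mean PID "differs from zero when the effect size is 0.56". It adds: "The effect size was calculated as the mean PID divided by the standard deviation". It gives neither the mean nor the SD. Section 7.2 states "The pain scores pre and post-treatment (after administration of the intranasal ketorolac [sprix]) will be compared" by t-test or F-test at p=0.05.

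Section 3.1 describes the trial as nonblinded, and all patients receive the drug. The design and analysis sections do not mention regression to the mean or untreated change in pain.

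**The concern.** A pain score is a patient's underlying level plus short-term fluctuation and reporting error. When a lower limit is applied to one reading, those who pass include some whose reading happened to be high, and some whose reading happened to be low are excluded. The next reading in the enrolled group is then lower on average, even with no treatment. If the reading used for entry is also the baseline for PID, that fall goes straight into the efficacy estimate.

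In the randomised trials summarised in 1.2, a placebo arm selected in the same way shows the same fall, and it cancels in the between-group comparison. Here nothing cancels it, and the null value is exactly zero. The bias always favours the drug. It is one of several non-drug contributions to PID, but one that a small change to the measurement schedule can reduce.

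**Working it through.** **1. The plan's own figure.** Two-sided normal approximation with n = 25 and effect size 0.56: power = Φ(0.56 × √25 − 1.96) = Φ(0.84) = 79.96%. The stated 80% reproduces, which confirms that the test is a one-sample (paired) comparison of PID with zero. The exact t calculation gives 76.6%, a separate minor matter.

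**2. Inputs for the bias.** From the plan: cut-off 40, n = 25, two-sided 0.05 (sidedness assumed). All else is assumed, because the documents give no pain-score mean, SD or repeat-score reliability for ED patients:
- mean before selection, μ: 55 to 65
- SD before selection, s: 22. The only anchor is the abdominal surgery trial in 1.2: SE 1.5 at 60 minutes in 214 ketorolac patients gives 1.5 × √214 = 21.9. It is a weak anchor, being a post-dose value in patients already selected at 40 or more. The SE of 1.9 at 20 minutes would give 27.8.
- reliability, r: 0.7 to 0.9
- no drug effect and no other change in pain

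**3. Formulas.** With z = (40 − μ)/s and λ = φ(z)/(1 − Φ(z)):
- spurious mean fall = (1 − r) × s × λ
- SD of PID = s × √[(1 − r)² × v + 1 − r²], where v = 1 + zλ − λ² is the variance factor after truncation
- false-positive rate = rejection probability of the two-sided t-test with n = 25 at standardised shift d = fall / SD of PID

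For μ = 55: z = −0.682, λ = 0.3162/0.7523 = 0.420, v = 0.537. For μ = 65: z = −1.136, λ = 0.2092/0.8721 = 0.240, v = 0.670.

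Example, μ = 55 and r = 0.7: fall = 0.3 × 22 × 0.420 = 2.77; SD = 22 × √(0.09 × 0.537 + 0.51) = 16.4; d = 0.169.

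| μ | r | Fall (points) | SD of PID | d | False-positive rate |
|---|---|---|---|---|---|
| 55 | 0.7 | 2.8 | 16.4 | 0.17 | 12.8% |
| 55 | 0.8 | 1.9 | 13.6 | 0.14 | 10.0% |
| 55 | 0.9 | 0.9 | 9.7 | 0.10 | 7.4% |
| 65 | 0.7 | 1.6 | 16.6 | 0.10 | 7.4% |
| 65 | 0.8 | 1.1 | 13.7 | 0.08 | 6.6% |
| 65 | 0.9 | 0.5 | 9.8 | 0.05 | 5.8% |

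Simulated paired t-tests agree with the last column to within 0.2 percentage points.

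**4. Sensitivity.** At μ = 70 with s = 22, the fall is 0.4 to 1.1 points. A wider grid (μ 50 to 70, s 20 to 25, r 0.5 to 0.9) gives 0.3 to 7.0 points, d of 0.03 to 0.30, and false-positive rates of 5.4% to 30%. The upper end needs many patients near the cut-off and poor reliability.

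**5. What a separate baseline does.** If the fluctuation in the two pre-dose scores is independent, the fall is about zero and the false-positive rate returns to about 5%. If fluctuation is serially correlated, with pre-dose scores 10 minutes apart and the post-dose score 60 minutes after the second, the scenarios tried removed about 22% to 76% of the bias. At μ = 50 and s = 20, 1.1 to 2.7 points remained, with false-positive rates of 5.7% to 13.7%.

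**The case against.** The strongest reply is that the plan does not say the two scores are the same. Section 4.2 places the baseline assessments after identification and consent, 3.2.1 ties eligibility to pain on presentation, 5.1.3 allows chart review, and the two scores in 5.1.4.2 are a minimum. A site could qualify a patient on the triage score and take a fresh baseline before dosing. This stands: a reader might infer that the protocol fixes the qualifying score as the PID baseline, and it does not. It leaves the matter open, while criterion 5 uses the word baseline for the qualifying score. A site that used one score for both would be compliant.

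A second reply is that the bias is a small part of a larger limitation. The trial is uncontrolled and nonblinded, and 5.1.4.4 allows other analgesics. PID against zero cannot isolate a drug effect with or without a second score. That also stands. It limits what the fix achieves but is no reason to keep a bias that can be reduced cheaply.

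A third is that a cut-off on baseline pain is common. It is, but a concurrent control usually absorbs the consequence, and there is none here.

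**Conclusion.** The point holds as a minor improvement. As written, the qualifying score may be the only pre-dose score and hence the PID baseline, and any regression to the mean then counts towards efficacy. Under the stated assumptions the size is about 0.5 to 2.8 points on 0 to 100, and the false-positive rate is about 6% to 13% if nothing else changes pain. If most patients present well above 40, it is less.

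Three stronger readings are not supported:
- That one repeat score would largely remove the bias. This needs independent errors between the two pre-dose scores. The documents give no figure for that, and scores taken minutes apart may share the same flare.
- That the bias is a known fraction of a planned effect in points. Section 7.1 gives only the ratio 0.56, so no planned effect in points exists to compare with.
- That regression to the mean alone could account for an effect of the size planned. The shifts in the table are 0.05 to 0.17 SD of PID, and at most 0.30 SD on the wider grid, against 0.56.

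**What to change.** In 3.2.2, reword criterion 5 so that eligibility rests on the triage or screening NRS. In 4.2 and 5.1.4.2, require a separate NRS immediately before the first spray, name it as the baseline for PID and SPID, and apply no analysis cut-off to it. The further apart the two scores are, the more of the bias is likely to go, which favours the triage score for eligibility. In 7.2, state that the result will be reported as change from baseline and not as drug effect, because natural easing, placebo response and co-treatment stay in PID whichever baseline is used.

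The cost is one extra NRS reading per patient. Some analysis baselines will fall below 40: about 4% to 13% under the assumptions above. The rewording of criterion 5 is essential, because 5.2 allows no deviations from the inclusion criteria and these patients would otherwise count as deviations.
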